## DONOR ELIGIBILITY AND CORNEA ASSIGNMENT

### EYE BANKS

### 3.1 Eye Bank Procedures

With the exception of procedures related to assignment of a cornea to a participant eye, specular microscopy external calibration and technician certification procedures and study procedures for obtaining specular images, eye bank procedures will mimic standard procedures as closely as possible to minimize disruption to their normal routine. Eye banks will be able to use any FDA-approved media for intermediate term storage up to 14 days at 4°C.

### 3.1.1 Donor Eligibility

526 All eye banks will follow their procedural routine for procurement of tissue and determination of  
527 suitability for EK, including prior LASIK or PRK donors, in accordance with the Medical  
528 Standards and Procedure Manual of the EBAA(19,20). This includes standard serologic testing,  
529 specular microscopy, and slit lamp examination.

531 The following eligibility criteria will apply to all donor tissue assigned to participant eyes:

- Obtained from an EBAA accredited eye bank
- Meets current EBAA and eye bank standards for human transplantation
- Age of donor at time of death 10-75 years
- If the donor body was refrigerated or eyes on ice within 10 hours of death, the body or eye may stay refrigerated up to  $\leq 20$  hrs; if no refrigeration then the death to preservation time should be  $\leq 10$  hrs
- Eye bank determined minimum ECD of  $\geq 2300$  cells/mm^2 (upon the initial screening determination of ECD)
- Polymorphism/Polymegethism: None to no more than mild changes (slight)
- Guttae: no true guttae present
- No evidence of central endothelial cell damage/trauma or dystrophy, such as FECD.

### 3.1.2 Assignment of Donor to Study Eyes

545 The primary eye bank, as designated by the clinical site, will receive a notification when there is  
546 a pending donor assignment. The Eye Bank Procedures Manual provides details regarding the  
547 assignment process. When the eye bank submits an assignment request, a computer program  
548 will use a minimization algorithm to evaluate all available donors and ensure a balance of  
549 subgroups (0-4 days, 5-7 days, 8-11 days, 12-14 days from preservation to surgery) within the  
550 primary randomization groups. Time from preservation to scheduled surgery date will be  
551 calculated as whole days for the purpose of assignment into the appropriate randomized  
552 preservation time group. As surgeons will be masked to all donor information, the label and  
553 report that accompanies the donor will be generated from the study website in such a way to  
554 maintain masking.

556 After the donor assignment procedure is completed, the eye bank will complete a donor  
557 information form on the study website, which includes information about the retrieval of the  
558 cornea (date/time of death, date/time of retrieval, aspects of the processing), cause of death, age  
559 of the donor, and ECD.

560

561 For those assignments where pre-cut tissue has been requested, the eye bank will cut and prepare  
562 the tissue on the same day that they would cut tissue if the donor was being assigned to a non-  
563 study participant for that particular surgeon, and will complete a cutting information form.

564

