## 268 1.2 Rationale

269 This study addresses an important public health issue related to the utilization of donor tissue for  
270 corneal transplantation and the need to increase and secure the donor pool. Similar to the bias  
271 which existed regarding donor age prior to the initiation of the CDS, the majority of corneal  
272 surgeons in the United States do not accept tissue with preservation time longer than 7 to 8 days,  
273 even though the FDA approval of Optisol GS, since its introduction in the early 90's, is for a  
274 preservation time of up to 14 days. Instead these corneas are exported to the international  
275 community where they are routinely transplanted up to 14 days of storage. A lack of  
276 information, particularly on a preservation time over 7 days, has likely contributed to a bias  
277 against using corneal tissue beyond this time. This study will address this bias by examining two  
278 parameters of long-term success: recipient corneal (stromal) clarity and endothelial cell density  
279 following EK (4) for the endothelial dysfunction conditions that have moderate risk for failure,  
280 FECD and PBK. Demand for corneas has substantially increased with the advent of EK.(1) In  
281 addition to the increased demand, there are additional areas of concern which may impact the

282 future donor supply including potential changes in the cornea evaluation process such as  
283 increased regulations and more extensive laboratory requirements to test for emerging infections,  
284 e.g. Hepatitis B and C, West Nile Virus, Chagas Disease.(2.3) By changing the practice pattern  
285 and increasing utilization of tissue beyond 7 days up to the FDA approved, 14 days from  
286 preservation to surgery, this will facilitate increasing the domestic donor supply enabling easier  
287 distribution of tissue and more time for tissue evaluation to rule out emerging infections with  
288 suspected donors.

289

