#### 303 **1.4.1. Study Design**

304 The CPTS is a randomized, controlled clinical trial examining the impact of preservation time on  
305 graft failure and endothelial cell density following EK. The study has been designed so that the  
306 surgeons and eye banks can follow and provide their usual surgical and post-operative  
307 procedures and care to study participants with the exception of assignment of donor tissue.  
308 Study eyes will be randomly assigned to receive a donor cornea from preservation date to  
309 surgery date of 8 to 14 days or a donor cornea from preservation date to surgery date of 7 or  
310 fewer days, with a comparable death to preservation time for both groups. Surgeons and study  
311 participants are masked to time from preservation to surgery.

312

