489 **2.5 Subject Enrollment**

490 A maximum of 1330 participants will be enrolled, depending on the number of participants who  
491 enroll both eyes into the study to reach the recruitment goal of 1330 study eyes with a goal to  
492 enroll an appropriate representation of minorities. As the enrollment goal approaches, sites will  
493 be notified of the end date for recruitment. Study participants who have signed an informed  
494 consent form can be randomized up until the end date.

495

496 After the informed consent form is signed, enrollment will be accomplished using the study  
497 website. Enrollment must be completed at least 10 days prior to the date of surgery. The study  
498 participant is then managed according to the investigator's usual routine without regard to the  
499 fact that the study participant is participating in the trial.

500 **2.6 Randomization**

501

502 Randomization of participant eyes will occur via an automated computer program. The  
503 randomization schedule will be stratified by surgeon using a permuted blocks design. The  
504 randomization groups are as follows:

505     • Preservation Time Group:  $\leq 7$  days  
506     • Preservation Time Group: 8-14 days

507

508

509 A study participant may have both eyes enrolled in the study. The eye scheduled for surgery  
510 which will occur first will be assigned randomly to a preservation time group, and the eye  
511 scheduled for surgery which will occur second will be assigned to the alternate group.

512

513

# Chapter 3

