#### 501 4.1.4 Analysis

502 An ANOVA model with 3 year ECD as the dependent variable will be used to assess  
503 the effect of preservation time.

- 504 505 • Confounding with regard to screening ECD is not expected to be an issue due to  
506 anticipated balance via randomization. Therefore, an ANCOVA model adjusting  
507 for eye-bank-determined screening ECD will only be used if this measurement is  
508 considered good enough to expect to have any impact on reducing variance.
  - 509 510 ○ Although all screening images are being collected, CIARC is not grading  
511 them other than a general quality assessment. CIARC will grade a sample  
512 of screening images within each eye bank. If more than 75% of the graded

509 ECDs are within 10% of the eye bank determined ECDs, the eye bank  
510 determined ECDs will be included in the model.

511 • The time from preservation to surgery will be treated as a binary variable.  
512 • If residual values from the models above are highly skewed then a transformation  
513 (e.g., square root or logarithm) or non-parametric methods will be used instead.  
514 • Random effects will be modeled to account for any correlated data from the same  
515 donor and any correlated data from 2 study eyes of the same study participant.  
516 • Additional ANCOVA models will also adjust for other recipient/donor risk  
517 factors. Univariate models will be evaluated first, and factors from those models  
518 with a p value <0.10 will then be evaluated in a multivariate model. A final model  
519 will be constructed consisting of factors with a p value <0.01 following a  
520 backwards selection process  
521 • Random surgeon effects will also be explored using a mixed effects model.  
522 • Sensitivity analysis will also be performed to check whether results change  
523 meaningfully depending on how missing data are handled. The missing 3 year  
524 ECD values for subjects with surviving grafts at 3 years will be imputed and  
525 included in an analysis as described in the previous section. The data imputation  
526 will be performed by using Rubin's method of multiple imputation.

527

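### Recipient eyes are randomised but corneas are not, and the main graft-failure model forces in no donor trait, so attributing the result to storage time itself can be confounded by donor mix

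*Combined protocol and SAP*

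**What the plan says.** **Allocation.** Protocol 2.6: "Randomization of participant eyes will occur via an automated computer program", and the "randomization schedule will be stratified by surgeon using a permuted blocks design". No donor factor enters at this step.

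**Choice of cornea.** Under protocol 3.1.2 a program "will use a minimization algorithm to evaluate all available donors and ensure a balance of" "subgroups (0-4 days, 5-7 days, 8-11 days, 12-14 days from preservation to surgery) within the" primary groups. Details of the process are left to the Eye Bank Procedures Manual, which is not among the documents. The form recording donor age, ECD and time of death comes later: "After the donor assignment procedure is completed, the eye bank will complete a donor" information form. Protocol 3.1.1 applies the same limits to all study tissue: donor age 10-75 years, screening ECD of at least 2300 cells/mm², and a cap on death-to-preservation time.

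**Expected balance.** Protocol 1.4.1 describes the short-storage arm as 7 or "fewer days, with a comparable death to preservation time for both groups". SAP 4.1.4 says "Confounding with regard to screening ECD is not expected to be an issue due to" the balance anticipated from randomisation. It adjusts 3-year ECD for screening ECD only if more than 75% of a sample of reading-center grades fall within 10% of the eye-bank values. Protocol 7.2.4.4 makes that adjustment without condition.

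**Graft failure.** The decision rests on the unadjusted Kaplan-Meier difference against 4 points (SAP 3.1.7). The primary multivariate Cox model contains storage group and corneal diagnosis (SAP 3.1.8). Donor age is among the confounders screened in additional models. Screening ECD is not on that list. Death-to-preservation time could at most fall under its general reference to retrieval and processing. Both are named as candidate predictors for Objective 3 (SAP 3.2.2). SAP 6.0 tabulates donor characteristics by arm.

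**The concern.** Randomising recipients balances recipient traits. It gives no such assurance for donors, because the cornea is drawn from whatever is held or can be imported in the assigned window. Selection is plausible: protocol 1.2 says most corneal "surgeons in the United States do not accept tissue with preservation time longer than 7 to 8 days" and that such tissue is exported. A cornea available on days 8-14 may have gone unplaced, or may have been kept for the study. The documents do not show which, so the direction of any donor difference is open.

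Two results depend on this. If 8-14 day donors were poorer, the trial could fail to show non-inferiority although storage does no harm. If they were better, harm from storage could be hidden. The same holds for 3-year ECD, where the SAP's stated reason for not needing the adjustment is a balance that the design does not secure.

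**Working it through.** **1. The plan's own figure.** Inputs from SAP 2.0: 6% failure in both arms, 4-point limit, one-sided 5%, 90% power.

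n per arm = (1.645 + 1.282)² × 2 × 0.06 × 0.94 / 0.04² = 604, so 1208 in total. This matches the plan.

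SE of the difference = √(2 × 0.06 × 0.94 / 604) = 1.37 points; power = Φ(0.04/0.01367 − 1.645) = 90.0%.

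**2. Effect of a donor-driven shift.** The documents give no size for donor imbalance or for its effect on failure. Let b be an assumed shift in the 8-14 day failure rate caused by donor mix alone.

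- Power when storage has no effect: Φ((0.04 − b)/SE − 1.645), rates 6% and 6% + b.
- Type I error when storage truly adds 4 points: Φ(−b/SE − 1.645), rates 6% and 10% + b.

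Worked example, b = +0.5: SE = √((0.06×0.94 + 0.065×0.935)/604) = 1.39 points; Φ(0.035/0.01393 − 1.645) = 80.7%.

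| Size of shift | Power, shift against 8-14 days | Type I error, shift favouring 8-14 days |
|---|---|---|
| 0 | 90.0% | 5.0% |
| 0.5 points | 80.7% | 9.4% |
| 1.0 point | 68.1% | 16.3% |
| 1.5 points | 53.5% | 26.2% |

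**3. What it takes to produce such a shift.** Assume a donor factor present in half of corneas, risk ratio r, mean failure 6%. Failure without the factor is p0 = 0.06/(0.5 + 0.5r), and an imbalance d in its prevalence gives b = d × p0 × (r − 1).

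| Imbalance d | r = 1 | r = 1.5 | r = 2 | r = 3 |
|---|---|---|---|---|
| 5 points | 0 | 0.12 | 0.20 | 0.30 |
| 10 points | 0 | 0.24 | 0.40 | 0.60 |
| 20 points | 0 | 0.48 | 0.80 | 1.20 |

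A half-point shift needs d = 0.005/(0.048 × 0.5), about 21 points, at r = 1.5, or 0.005/(0.03 × 2), about 8 points, at r = 3. These calculations ignore correlation between paired eyes and between corneas of one donor.

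**4. Which traits have an assured place in the analysis.** In the primary multivariate failure model, none. Donor age must pass the SAP 3.1.8 screening, which ends in p<0.10 and then p<0.01 selection. Those thresholds respond to strength of association with failure, so a trait that shifts the storage effect can still be dropped. Screening ECD and death-to-preservation time reach failure models by name only through SAP 3.2.2, with the same thresholds for the multivariate model.

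**5. Treatment of screening ECD.** Protocol 7.2.4.4 adjusts always; SAP 4.1.4 adjusts conditionally; SAP 4.3 adjusts pre-operative ECD for the same measure with no condition.

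**The case against.** Several points on the other side stand.

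- A reader might infer that the algorithm ignores donor traits. The documents do not show that. The procedures manual may say more, and the later donor form does not prove the data were missing at assignment, because age, screening ECD and death-to-preservation time are eligibility criteria that the eye bank must already know.
- A reader might infer that donor traits are absent from the failure analyses. They are not. SAP 3.1.8 names donor age; SAP 3.2.2 lists all three traits for Cox models that include storage group; SAP 6.0 would make an imbalance visible. What is missing is an adjustment that does not depend on p-values.
- It is tempting to size the problem through donor age. The documents' one outcome result on it points the other way: the Cornea Donor Study found 86% success at 5 years in both donor-age groups (protocol 1.1, in penetrating keratoplasty). Screening ECD and death-to-preservation time are the stronger candidates. Protocol 1.1.1 reports more stromal edema and folds with longer death-to-preservation time in that study.
- A reader might conclude that the randomised comparison is invalid. It is not, for the policy of assigning recipients to 8-14 day tissue as supplied.
- Shared donor limits bound any imbalance, and surgeons are masked to most donor information.

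These points narrow the concern without removing it. A table shows an imbalance but does not correct for it, and protocol 1.2 and 6.1 intend the result to be read as the effect of preservation time.

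**Conclusion.** The point holds in this form: donor traits can differ between arms, randomisation of recipients does not prevent it, and the planned failure analysis guarantees no adjustment for them. The statement in SAP 4.1.4 that randomisation should balance screening ECD is not supported by the design described, and it accompanies a weakening of the adjustment set in protocol 7.2.4.4.

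The size of any bias is unknown. Type I error of 9.4% to 16.3%, or power of 81% to 68%, follows from assumed shifts of 0.5 to 1.0 point with 604 evaluable eyes per arm and 6% failure. With balanced donors, or traits unrelated to failure, the effect is zero. The inflated error concerns the claim about storage itself, and no stated sample-size figure is wrong. That the storage-day band is the sole balancing target is a reading of the protocol text, subject to the manual.

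**What to change.** 1. **SAP 3.1.8.** Force donor age, eye-bank screening ECD and death-to-preservation time into the primary multivariate model beside corneal diagnosis, whatever their p-values. All three are fixed before storage. A hazard ratio cannot be read against a 4-point limit, so also report a supportive donor-adjusted 3-year risk difference (for example, model-based failure probabilities averaged over all eyes under each arm), with the same bootstrap one-sided 95% interval, beside the unadjusted primary result. Do not use the reading center's pre-operative ECD for this: it is measured after storage and may carry part of the storage effect.
2. **SAP 4.1.4.** Remove the randomisation-balance rationale and restore the unconditional adjustment for screening ECD in protocol 7.2.4.4.
3. **Protocol 3.1.2.** State whether the algorithm uses donor traits. If assignment is still open, add donor age and screening ECD as balancing factors where more than one eligible cornea is available.

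**Cost.** The covariates are already collected. About 0.06 × 1208 = 72 to 0.06 × 1330 = 80 failures are expected. With storage group, diagnosis and three linear donor terms, that is at least 72/5 ≈ 14 per coefficient. The adjusted difference requires refitting the model in each resample. Where only one eligible cornea exists, the algorithm cannot balance and the adjustment must do the work.

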### 565 **3.1.2.1 Donor Not Available**

566 If an eligible donor in the correct preservation time window is not available at the primary eye  
567 bank on the date of assignment, attempts will be made by the primary eye bank to import tissue  
568 from another EBAA accredited eye bank. If tissue in the correct preservation time window is  
569 still not available, it will be up to the surgeon to either (1) reschedule the surgery or (2) inform  
570 the participant that they will receive a donor that is otherwise healthy but does not meet criteria  
571 to be in the study and that they will be discontinued from the study.

572

### 573 **3.1.2.2 Rescheduled Surgery and/or Reassignment of Tissue**

574 If the surgeon rejects the assigned donor cornea for any reason, surgery will be rescheduled, and  
575 a new assignment will be completed.

576 If surgery is rescheduled for any reason, and an already assigned donor cornea is no longer in the  
577 correct preservation time window, a new assignment will be completed.

578

### 579 **3.1.3 Eye Bank Procedures for Study Images**

580 Detailed procedures for obtaining best image quality and transmission to the DMAC will be  
581 provided in the CPTS-CIARC Calibration, Certification, and Study Imaging Clinical Procedure  
582 Manual and the technician(s) performing this procedure will be certified by the Cornea Image  
583 Analysis Reading Center (CIARC).

584

#### 585 **3.1.3.1 Screening Images**

586 Up to 3 screening images of the central donor corneal endothelium obtained according to the eye  
587 bank's usual procedure should be submitted to the DMAC.

588

#### 589 **3.1.3.2 Pre-Operative Images**

590 Three pre-operative images of the central donor corneal endothelium should be obtained in a  
591 viewing chamber by a certified technician, and submitted to the DMAC. If the eye bank is  
592 performing the cutting, the eye bank should obtain these pre-operative images after the tissue has  
593 been cut. If the surgeon is performing the cutting, the eye bank should obtain these pre-operative  
594 images as close as possible prior to shipment to the surgeon following appropriate warming to  
595 room temperature.

596

597  
598  
599  
600

## Chapter 4 TRANSPLANTATION AND FOLLOW UP CLINICAL SITES

601  
602  
603  
604  
605  
606  
607

### **4.1 Endothelial keratoplasty procedure**

Surgery (DSEK, DSAEK) will be performed according to the investigator's usual routine. Aspects of the surgical technique and procedure will be tracked, but not standardized. Data to be collected will include incision size, insertion method, air usage, other procedures (e.g. cataract surgery), and operative complications (e.g., difficult donor preparation, difficult placement). *As a reminder, the DMAEK and DMEK procedures will not be acceptable endothelial keratoplasty procedures for the CPTS nor will be PKP.*

608  
609  
610  
611  
612

The surgeon will be masked to donor parameters (e.g. donor age, donor ECD), except the FDA-approved 4°C preservation medium being employed (Optisol GS, Life 4°C, etc.) and parameters needed to perform the surgery (e.g. post-cut thickness). Most importantly the surgeon and study participant will be masked to preservation time.

613  
614  
615  
616  
617

### **4.2 Post-operative Management**

Postoperative management will be at the discretion of the surgeon based on his/her usual practices. Key aspects of pharmacologic management (e.g. topical corticosteroid usage) will be collected on the data forms.

618  
619  
620

### **4.3 Follow-up visit schedule**

Protocol-specified follow-up visits (and visit windows) for the first eye, established to conform to the usual practice and timed from surgery date, will be as follows:

621  
622  
623  
624  
625  
626  
627

- Day 1 (1-2 days)
- Day 7 (5 – 9 days)
- Day 30 (20-40 days)
- 6 months (4-8 months)
- 12 months (10-14 months)
- 24 months (20 - 28 months)
- 36 months (35 – 42 months)

628  
629  
630  
631

Additional visits can be performed more often at the discretion of the investigator. A data form will be completed for each protocol and non-protocol visit. For example, if graft failure is determined and a regraft is required on a non-protocol visit, the appropriate follow-up visit form and graft failure form should be completed if and when this occurs.

632 If the second eye of an active participant is enrolled, a modified visit schedule will be allowed  
633 to minimize return visits for participants that had bilateral EK as part of the study. For example,  
634 sites will be allowed to follow standard of care practices to avoid unnecessary visits linked to  
635 targeting each eye within its respective windows as listed above. Sites are encouraged to  
636 schedule both eyes within their respective windows when the windows overlap, but at minimum  
637 at least one eye must be within its target visit window at each visit. The only exception to this is  
638 the 36 month visit which must be completed for each eye within its respective window, even if  
639 an extra return visit is required.

640 **4.4 Testing procedures**

641 The Table below shows the key elements of data collection at each study visit. Additional visits  
642 may occur as needed for the usual care of the participant.

643

Parameters	Pre-op	1 Day	1 Week	1 Month	6 Months	12 Months	24 Months	36 Months
Medication History	X	X	X	X	X	X	X	X
Slit lamp examination	X	X	X	X	X	X	X	X
Intraocular pressure	X		X	X	X	X	X	X
Ultrasonic pachymetry			X	X	X	X	X	X
Endothelial imaging					X	X	X	X
Post-op complications and other untoward events		X	X	X	X	X	X	X

644

645 **4.5 Definition of testing procedures**

646 **4.5.1 Slit Lamp Examination**

647 The slit lamp examination should be performed per the investigator's usual routine. Specific  
648 details of the data collected during the slit lamp examination are found in the site procedures  
649 manual.

650

651 **4.5.1.1 Recipient corneal stroma clarity**

652 The recipient corneal stroma clarity will be assessed by slit lamp examination using the  
653 following 3-level classification:

654

655 • clear central recipient stroma;  
656 • equivocally cloudy central recipient stroma  
657 • clouded central recipient stroma.

658

659 Specific details regarding the grading of recipient corneal stroma clarity are found in the Site  
660 Procedures Manual. Investigators will be provided a high resolution color standard scale and will  
661 be trained and certified on this classification scheme prior to enrolling participants.

662  
663 **4.5.1.2 Donor corneal stroma clarity**  
664 Donor corneal stroma clarity will be assessed by slit lamp examination. Specific details  
665 regarding the grading of donor corneal stroma clarity are found in the Site Procedures Manual.  
666

667 **4.5.1.3 Graft rejection assessment**

668 Graft rejection will be assessed during the slit lamp examination using a modification of the  
669 Collaborative Corneal Transplantation Studies (CCTS) classification (21,22). Graft rejection will  
670 be classified as definite, probable/ possible, or not present. Details of the assessment of graft  
671 rejection are found in the Site Procedures Manual.

672 The management of suspected graft rejection episodes will be according to the investigator  
673 prerogative, but documented in the medication history.  
674

675 **4.5.2 Intraocular pressure**

676 Intraocular pressure will be measured using the investigator's usual routine.

677 **4.5.3 Ultrasonic pachymetry**

678 Corneal thickness will be measured by a CPTS-provided ultrasonic pachymeter to ensure  
679 standardization of this measurement across sites. Technical staff acquiring this measurement will  
680 be trained and certified on study pachymeter use. If no measurement can be obtained (e.g. if the  
681 cornea is too thick), this will be noted on the data form. Measurements taken on other  
682 pachymeters will only be allowed if the study pachymeter is temporarily not functional.

683 **4.5.4 Specular/confocal microscopy**

684 Specular or confocal microscopy of the central endothelium will be obtained on all participants  
685 that have not experienced graft failure to determine ECD by CIARC. Detailed procedures for  
686 obtaining best image quality and transmission to the DMAC will be provided in the CPTS-  
687 CIARC Calibration, Certification, and Study Imaging Clinical Procedure Manual and the  
688 technician(s) performing this procedure will be certified by the CIARC.

689 **4.6 Additional procedures**

690 Data on all additional procedures performed on the study eye will be collected, including:

691 • air bubbling/repositioning in the first month  
692 • cataract surgery and placement of intraocular lens (anterior chamber, posterior chamber)  
693 • YAG capsulotomy

694       • refractive procedure (e.g. limbal relaxing incision, LASIK)  
695       • glaucoma surgery (e.g. trabeculectomy, laser trabeculoplasty, tube shunt, mini-shunt, other)

696       Additionally, data on donor tissue rim cultures may be collected if performed as part of standard  
697       of care.

698

